5. STUDY PURPOSE

The time to defibrillation is the single most critical determinant of survival in SCD. Survival rates after VF decrease approximately seven to ten percent with every minute that defibrillation is delayed.⁵ While rapid defibrillation with an Automated External Defibrillator (AED) by nonmedical personnel can improve survival after out-of-hospital cardiac arrest, the time period between arrest and successful resuscitation must be short and the cardiac arrest must be witnessed. The development of a wearable cardioverter defibrillator has provided a new therapy option for patients who are at high risk of SCD and may require a defibrillation shock without the assistance from a bystander.

The Jewel System is an automatic external defibrillator which monitors patients at risk for SCD and provides a therapeutic shock if needed. The Jewel System is intended to be worn at home or in the hospital during temporary periods of time when ICD implantation is commonly deferred.

To date, ZOLL is the sole manufacturer of a commercial product approved as a wearable automated external defibrillator. The ZOLL LifeVest WCD is currently available in the United States, Europe, Australia, Israel, Japan, and Singapore.

The clinical efficacy of external defibrillation shock waveforms used in the ZOLL LifeVest WCD and other AEDs has been studied routinely in the controlled environment of the EP lab. For example, with the replacement of monophasic damped sine waveforms with lower energy biphasic truncated exponential waveforms, clinical efficacy was compared by measuring first shock success rate in patients undergoing electrophysiologic testing.⁶ With the ZOLL LifeVest WCD, the clinical efficacy was also evaluated as part of a routine EP procedure in which ten (10) patients were induced into VF and the LifeVest was used to deliver a single defibrillation shock.⁷ In this study, special WCD units were used that were manually charged and discharged by the physician to terminate the VF episode in a relatively short time period (mean duration of 32 seconds per episode).

Similar to the ZOLL LifeVest and AEDs, the Jewel System is designed to deliver a fixed energy of approximately 150 joules using a biphasic truncated exponential waveform that is adjusted based on the transthoracic impedance of the patient. The purpose of this clinical study is to demonstrate the safety and effectiveness of the Jewel EP Lab System to deliver a single transthoracic defibrillation shock to terminate life-threatening VT or VF.

The study is planned to be conducted in standard clinical cases, such as an EP study or an ablation case, in which life-threatening VT or VF may spontaneously occur or be induced. As with similar EP lab studies, the duration of life-threatening VT or VF will be limited to a relatively short time period (less than 20-30 seconds) to minimize the safety risk to the patient since the duration of life-threatening VT or VF has been shown to be inversely proportional to the success of defibrillation

⁵ American Heart Association. 2005 American Heart Association Guidelines for Cardiopulmonary Resuscitation and Emergency Cardiovascular Care. *Circulation*, Supplement 2005.

⁶ Bain et.al. Multicenter study of principles-based waveforms for external defibrillation. *Annals of Emergency Medicine*, Jan 2011: 37:1, 5-12.

⁷ Auricchio, A. et.al. "Clinical Efficacy of the Wearable Cardioverter-Defibrillator in Acutely Terminating Episodes of Ventricular Fibrillation." *Amer J Cardiol*. 1998; 81: 1253-1256.

therapy.^{8,9} Unlike the Jewel EP Lab System, the Jewel System is designed for ambulatory patients and therefore if the system detects a shockable rhythm, the firmware initiates the alarm sequence, allowing a conscious patient to have time to respond and press the Control Buttons to prevent delivery of a shock (approximately 50-60 seconds from the initial detection of the shockable rhythm). Although this is acceptable for an out-of-hospital event, the Jewel EP Lab System is a derivative of the Jewel System designed for the EP lab environment to allow the clinical user to manually charge the capacitors and trigger the delivery of the defibrillation shock at any time during the procedure. The Jewel EP Lab System does not require waiting for the algorithm to detect and classify a shockable rhythm. This ensures that the clinical user has full control of the delivery and timing of the therapeutic shock in order to avoid a prolongation of the response time during the acute EP lab procedure.

In this study, the EP lab procedure is a standard clinical procedure that follows the standard of care at the hospital facility. The clinical presentation of life-threatening VT or VF and the clinical guidelines for defibrillation do not differ between European or US clinical sites.

The results of the VEST trial, a randomized controlled trial (RCT) of over 2,300 subjects comparing the ZOLL LifeVest to Guideline Directed Medical Therapy, were reported at the American College of Cardiology Conference in March 2018, and in the New England Journal of Medicine on 27 September 2018.¹⁰ In this RCT, there were a total of 21 appropriate shocks, of which 13 were converted with the first shock and 8 of which required ≥ 2 shocks (38%). This translates into a 62% first shock success rate.¹¹

⁸ Windecker, S et.al. The influence of ventricular fibrillation duration on defibrillation efficacy using biphasic waveforms in humans. *Journal of the American College of Cardiology*, Volume 33, Issue 1, January 1999, 33-38.

⁹ Winkle, R et.al. Effect of duration of VF on defibrillation efficacy in humans. *Circulation*, Vol 81, No 5, May 1990, 1477-1481.

¹⁰ Jeffrey E Ogin et al., “Wearable Cardioverter–Defibrillator after Myocardial Infarction,” *N Engl J Med*, 2018, 11.

6. STUDY DESIGN

This study is a single center, prospective, single arm, non-randomized, non-blinded feasibility study that will be conducted in the European Union. The sample size for the study is a maximum of 24 subjects.

Eligible subjects will be those scheduled for a standard EP procedure where life-threatening VT or VF may spontaneously occur or may be induced. Subjects are excluded if they exhibit a left ventricular ejection fraction (LVEF) less than 20%, have been recently diagnosed with heart failure or have NYHA Class IV heart failure, have unstable angina or atrial fibrillation with a contra-indication to anticoagulation or improper anticoagulation management. The adaptive study design will allow for continuous enrollment of eligible subjects until the sample size is met for the treatment analysis per the statistical plan.

Patients undergoing a standard EP clinical procedure where life-threatening VT or VF may occur are eligible for enrollment in this study. The Jewel EP Lab System will be placed on the subject's torso in the anterior-apical monitoring vector and will be able to deliver an electric shock in the event the patient experiences spontaneous or induced VT or VF.

It is anticipated that the study will require 3 months for enrollment and completion as the study does not require follow-up after the completion of the EP Lab procedure except in the event of adverse events in which case the subject will be followed until resolution. The Sponsor and the Principal Investigator will continuously monitor the safety data (including all reported serious adverse events) throughout the trial.

6.1. PRIMARY EFFICACY ENDPOINT

The primary endpoint will evaluate the percent of successful terminations of life-threatening VT or VF in subjects who are enrolled in compliance with the protocol-defined entry criteria and are treated with either model of the Jewel EP Lab System. The endpoint will be achieved if the lower confidence limit exceeds the performance goal of 62% using a one-sided exact lower 97.4% confidence bound at one of three testing points. These conditions ensure that performance will be in line with previously published randomized controlled trial results on a relevant comparator, the ZOLL LifeVest, which is the only commercially approved WCD in Europe or the United States. A sequential method of testing will be used to evaluate conversion success. If the Jewel EP Lab System is NOT used to deliver a defibrillation shock during the EP procedure, the subject will not be included in the treatment analysis.

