7. STUDY POPULATION

7.1. PATIENT INCLUSION/EXCLUSION CRITERIA

The study will only enroll up to 24 subjects that fulfill the eligibility criteria of the investigation. Subject participation is voluntary and the study will be conducted in accordance with the Declaration of Helsinki.

Inclusion Criteria:

Candidates for this study must meet all the following criteria:

- 1) Subjects of both genders of at least 18 years of age.
- 2) Subjects who are scheduled for a standard EP clinical procedure where life-threatening VT or VF may spontaneously occur or may be induced.

Exclusion Criteria:

Candidates will be ineligible for enrollment if any of the following conditions apply:

- 1) Subjects who may require sterile access to the right upper pectoral or lower left torso regions during the planned EP procedure.
- 2) Subjects who have taken amiodarone in the past 3 months.
- 3) Subjects with an existing unipolar pacemaker.
- 4) Subjects who exhibit a left ventricular ejection fraction (LVEF) less than 20% (as assessed by techniques such as echocardiography, magnetic resonance imaging, or radionuclide angiography within the last 6 months).
- 5) Subjects who have been diagnosed with heart failure (Class IV) or experienced an acute heart failure exacerbation within the previous 30 days.
- 6) Subjects who exhibit unstable angina.
- 7) Subjects with atrial fibrillation with contraindication to anticoagulation or improper anticoagulation management.
- 8) Subjects who are participating in an investigational study of a drug, biologic, or device not currently approved for marketing.
- 9) Subjects who are allergic to or have had a known adverse reaction to medical adhesives.
- 10) Subjects who have active skin breakdown, erythema, or other signs of infection in the pectoral or torso regions where the study device is applied.
- 11) Subjects with a lower abdomen circumference of less than 68.5 cm or greater than 142 cm.
- 12) Females who are pregnant or breastfeeding, or planning to be pregnant in the next 12 months.
- 13) Subjects who cannot provide or have diminished capacity to provide informed consent.
- 14) Any condition that an Investigator believes would interfere with the intent of the study or is not in the best interest of the patient.
- 15) Any patient that according to the Declaration of Helsinki is unsuitable for enrollment.

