Prior to the onset of life-threatening VT or VF, the hospital staff will prepare the Jewel EP Lab System by initiating the device charge cycle. The user will depress the "CHARGE" button on the Controller Box to charge the capacitors for delivery of the defibrillation shock. Charging will take approximately 20 seconds during which the Controller Box will display a flashing green "CHARGE" light. The rescue defibrillator will also be prepared for use should the Jewel EP Lab System not deliver an electrical shock or fail to terminate VT/VF.

Upon completion of charging, the Jewel EP Lab System will display a solid green "CHARGE" light on the Controller Box. After the device is charged, the user will be able to manually deliver a

defibrillation shock through the Jewel EP Lab System by depressing the “SHOCK” buttons on the Controller Box.

Throughout the procedure, the Jewel EP Lab System will continuously monitor the ECG signal, and the Controller Box will illuminate the “DETECT” yellow light to notify the user when the algorithm has detected life-threatening VT or VF. The detection algorithm continuously analyzes the ECG signal in segments of eight seconds and determines whether a shockable rhythm is present in the majority of that segment after the entire segment has finished. Based on the timing of the onset of VT/VF relative to ECG segments, the algorithm may require up to 8-12 seconds of ECG signal to capture a full eight-second segment for determination of a shockable rhythm. If a shockable rhythm is detected, the light indicator on the Controller Box will flash a yellow light continuously. If the VT/VF is sustained through a second eight-second segment, the light indicator will change to a solid yellow light. At any time during this process, irrespective of algorithm determination, the defibrillation shock may be delivered using the “SHOCK” buttons on the Jewel EP Lab System. Although the performance of the detection algorithm is not a primary endpoint in this study, the status of the detection light will be recorded during the case.

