In cases where the patient is stable, the VT/VF may be allowed to continue for 20-30 seconds to ensure the algorithm has sufficient ECG data to make a rhythm determination over multiple eight-second segments. The timing of the defibrillation shock is under the discretion of the physician to ensure patient safety. In the case where VT/VF is not sustained for the minimum of 8-12 seconds, the indicator light on the Controller Box will not illuminate. The ECG data recorded on the Jewel EP Lab System will also be analyzed post-procedure to assess the performance of the algorithm.

In the event that the defibrillation shock delivered through the Jewel EP Lab System does not successfully terminate the VT/VF, the rescue defibrillator will be used to deliver subsequent defibrillation shock(s).

Throughout the clinical procedure, the Jewel EP Lab System will only be used in appropriate cases based on physician judgment.

- In the case that a defibrillation shock is delivered through the Jewel EP Lab System, the clinical procedure will continue as planned. If a subsequent defibrillation shock is required during the procedure, the rescue defibrillator will be used. The Jewel EP Lab System will only be employed for a single shock during each procedure. In the case that the Jewel EP Lab System is used to deliver a defibrillation shock and the subject meets all enrollment criteria, the subject will be included in the treatment analysis for the primary endpoint.
- In the case that the Jewel EP Lab System is not used to deliver a defibrillation shock during the procedure, the subject will not be included in the treatment analysis to meet the sample size requirements per the statistical plan. In approximately 30 percent of cases, life-threatening VT or VF may not occur or be inducible and therefore an external defibrillation shock would not be required.¹¹ In addition, based on physician judgment, the Jewel EP Lab System may not be used to provide a defibrillation shock during the procedure. In these cases, the subject will not be included in the treatment analysis for the primary endpoint, however, an Intent-to-Treat (ITT) analysis will be performed for informational purpose.

At the conclusion of the acute procedure, the Jewel EP Lab System will be removed from the subject and the Controller Box will be disconnected from the Adhesive Electrode Patches. The subject will exit the study immediately after completion of the EP clinical procedure.

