9. SUBJECT REMOVAL FROM STUDY

Only subjects that meet all enrollment criteria and have received a defibrillation shock will be included in the treatment analysis, however all subjects enrolled, whether or not receiving a defibrillation shock, will be included in the reporting of study results.

Overall, if a subject drops out of the study at any time due to an adverse event or for any other cause, the reason for discontinuation, the nature of the event, and its clinical course must be fully followed and documented. In the case of an adverse event, the Investigator must strive to follow the subject until the adverse event has either resolved, become clinically insignificant, the event is stabilized, or the subject is lost to follow-up.

If at any point during the study, the patient withdraws consent or the Investigator assesses that the risks to the subject outweigh the benefits of participation in the study, the subject will be discontinued. If, during the course of the study, the Investigator feels that, in his/her best clinical judgment, the study should be prematurely terminated, he/she will notify the Sponsor and give the reason(s) for this decision. If the Sponsor decides, based on data or internal information, that it would be prudent to discontinue temporarily or to terminate the study, the Sponsor will inform the Investigator of this decision and the reason(s) for the decision.

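### The plan does not say how a Jewel shock that is commanded but does not fire is scored: the inclusion rules, read literally, drop it, while the testing steps can be read to count it as a failure

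*Combined protocol and SAP*

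**What the plan says.** Three sections of the combined protocol and SAP define who enters the treatment analysis.

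- Section 6.1 gives this rule: "If the Jewel EP Lab System is NOT used to deliver a defibrillation shock during the EP procedure, the subject will not be included".
- Section 8.2 repeats the rule and gives two circumstances. The first, put at roughly 30 percent, is that "life-threatening VT or VF may not occur or be inducible and therefore an external defibrillation shock would not be required". The other is discretion: "In addition, based on physician judgment, the Jewel EP Lab System may not be used to provide a defibrillation shock during the procedure".
- Section 9: "Only subjects that meet all enrollment criteria and have received a defibrillation shock will be included in the treatment analysis". The device that gave the shock is not named.

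Section 8.2 also anticipates non-delivery. The rescue defibrillator is made ready "should the Jewel EP Lab System not deliver an electrical shock or fail to terminate VT/VF", so non-delivery is listed apart from failure to terminate. Only the rescue action follows; no score is given.

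Section 11.1 uses different terms. Its steps are applied once conversion has been attempted in 12 and then in 24 subjects, and the trial stops as unsuccessful after more than three failures to convert that are due to the Jewel. Neither requires that a shock was delivered.

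On replacement, Section 6 allows "continuous enrollment of eligible subjects until the sample size is met for the treatment analysis per the statistical plan", whereas Section 7.1 says "The study will only enroll up to 24 subjects that fulfill the eligibility criteria of the investigation".

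**The concern.** A device that is told to shock and does not has not terminated the rhythm. If such a subject leaves the denominator, the endpoint becomes conversion given that the device fired, and device failures drop out of the device's own effectiveness rate. That can only raise the observed rate.

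The two sets of wording can also split: one non-fire could count towards the more-than-three-failures stop yet be absent from the success rate. In an unblinded single-arm study of at most 24 subjects, a single reclassified subject can decide a look. Since the text supports either scoring, the choice could be made with the result in view.

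**Working it through.** **Inputs, all from Section 11.1 unless noted.** Performance goal 62%; anticipated rate 87.5%; one-sided 97.4% Clopper-Pearson bound (one sentence says 94.5%; the worked bounds use 97.4%); success at 12/12, at 16/18 or better, or at 21/24 or better; stop at the fourth failure. No VT/VF in about 30% of cases (Section 8.2). The non-delivery rate is not given, so any value is an assumption.

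**Step 1. The plan's bounds reproduce.** The lower bound is the 0.026 quantile of Beta(x, n − x + 1). For 12/12 it is 0.026^(1/12) = 0.738.

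| Result | Bound computed | Bound in plan |
|---|---|---|
| 12/12 | 73.8% | 73.7% |
| 17/18 | 72.9% | 72.8% |
| 16/18 | 65.5% | 65.4% |
| 21/24 | 67.8% | 67.8% |

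**Step 2. One non-fire takes the place of one success.**

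- 12/12 becomes 11/12: bound 61.8%, below 62%, so continue.
- 17/18 becomes 16/18: bound 65.5%, still a success.
- 16/18 becomes 15/18: bound 58.8%, so continue.
- 21/24 becomes 20/24: bound 62.8%. This exceeds the goal, but it misses the 21/24 step and is a fourth failure.

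**Step 3. Written rule with no non-fires counted (exact binomial over the three looks).**

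- At 62%: 0.0032 + 0.0108 + 0.0019 = 0.016 after rounding, the Type I error per delivered shock.
- At 87.5%: 0.2014 + 0.4095 + 0.0941 = 0.705. This is not the 90% power stated in Section 11.1, which is a separate matter.

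**Step 4. Exactly one non-fire, every dropped subject replaced, delivered shocks converting at 87.5%.** If the non-fire is dropped, the chance of success stays at 0.7051. If it is counted:

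- *Among attempts 1-12.* Look 1 cannot succeed. Look 2 needs at most 1 failure in 17 delivered shocks: 0.875^17 + 17 × 0.125 × 0.875^16 = 0.1033 + 0.2509 = 0.3542. Look 3 needs exactly 2 failures in those 17 and none in the next 6: 136 × 0.125² × 0.875^21 = 0.1287. Total 0.4829. Loss: 0.7051 − 0.4829 = 0.222.
- *Among attempts 13-18.* Look 1 is unaffected: 0.2014. Look 2 needs one failure in the first 12 and none in the other 5: 12 × 0.125 × 0.875^16 = 0.1771. Look 3 needs two failures in 17, not both in the last 5, then none in 6: (136 − 10) × 0.125² × 0.875^21 = 0.1192. Total 0.4977. Loss: 0.207.
- *Among attempts 19-24.* Looks 1 and 2 are unaffected. All of look 3's 0.0941 is lost, because a path that reaches look 3 and would succeed there already has three failures.

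Scoring the same attempts both ways shows that, for attempts 1-12, success also moves to a later look in 30.6% of trials and nothing changes in 47.2%. With replacement, no trial moves from failure to success.

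**Step 5. Enrolment capped at 24, 30% without VT/VF, one non-fire among the first 12 attempts.** Success requires that a look is reached. Counting then turns success into no success in 17.9% of trials and no success into success in 2.8%. An example of the reverse is 18 attempts with one non-fire, one early conversion failure and 16 conversions. Counted, this is 16/18 and a success. Dropped, it is 16/17 and the second look is never reached.

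**Step 6. Price of counting, with replacement.** At an assumed 2% non-delivery the rate per attempt is 0.875 × 0.98 = 0.8575 and the chance of success is 61.4%. At 5% it is 0.875 × 0.95 = 0.83125 and 47.9%. Both compare with 70.5%.

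**The case against.** The best defence is that the exclusion was never meant for misfires. The protocol often says the device is used to do something in the sense of purpose, so a device not used to deliver a shock may simply be one the operator did not call on. Both circumstances in Section 8.2 fit that, and the operative steps in Section 11.1 speak of attempts. This shows that the plan does not positively direct non-fires to be dropped, though a reader might infer that it does. It does not close the gap: no section limits the exclusion to untried cases, a misfire fits neither circumstance, and Section 9 asks for a received shock.

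Second, non-fires would be seen, through device-deficiency reporting (Sections 10.1 and 10.2) and the reporting of all enrolled subjects (Section 9). That stands against any suggestion that they would be hidden. But neither of these, nor the informational ITT analysis, sets the primary denominator.

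Third, the 62% goal is 13 of 21 delivered shocks (Section 11.1), so a delivered-shock denominator is like for like. That is a fair reason to prefer it, provided it is stated in advance.

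A reader might also infer that Type I error is inflated. Against the stated goal it is 1.6% whatever the non-delivery rate. It exceeds 5% only if the goal is read per attempt, which the protocol does not do, and non-delivery is high: 6.2% at an assumed 10%.

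**Conclusion.** The gap is real. Applied literally, the inclusion rules remove device failures from the device's effectiveness rate, and other text supports the opposite scoring. It is a defect in the endpoint definition, not a breach of the error limit.

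The sizes of 22.2%, 20.7% and 9.4% are conditional on one non-fire having occurred, on 87.5% conversion of delivered shocks and on full replacement. They are not the chance that this trial is affected, which cannot be given without a non-delivery rate. Nor does the trial verdict always move one way. The observed rate can only rise when non-fires are dropped, but under the cap of 24 enrolled about 18% of trials lose success by counting and about 3% gain it. At the last look, 20/24 fails the step and stopping rules, not the 62% bound.

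Classification: cheap improvement.

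**What to change.** State before the first look:

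- The primary set is all eligible subjects with life-threatening VT/VF in whom a Jewel shock was commanded (SHOCK pressed). A trigger based on charging would be harder to adjudicate, because Section 8.2 has charging precede onset.
- Non-delivery counts as a failure in both the success rule and the more-than-three-failures rule.
- Only two groups are excluded: subjects with no VT/VF, and subjects in whom the physician chose not to use the device for a reason other than a device fault during the episode. Both are listed with reasons.
- The delivered-shock rate is a sensitivity analysis, to match the comparator. If the sponsor prefers it as primary, that should be declared in advance and the per-attempt rate reported beside it.

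Align Sections 6.1, 8.2, 9 and 11.1. This changes scoring only, not conduct of the procedure.

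The cost is wording and perhaps one CRF field for the shock command. The denominator becomes slightly stricter than the comparator's, and the chance of success falls if the device misfires, by the amounts in step 6 of the working.
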